8.3.2.1.2. Definition of Serious Adverse Event

An AE is considered serious if, in the view of either investigator or sponsor, it results in any of the following outcomes:

- Death,
- A life-threatening AE,

An AE is considered “life-threatening” if, in the view of either the investigator or sponsor, its occurrence places the patient or subject at immediate risk of death. It does not include an AE that, had it occurred in a more severe form, might have caused death. The determination of whether an AE is life-threatening can be based on the opinion of either the investigator or sponsor. Thus, if either believes that it meets the definition of life-threatening, it must be considered life-threatening for reporting purposes.

- Inpatient hospitalization or prolongation of existing hospitalization,
- A persistent or significant incapacity or substantial disruption of the ability to conduct normal life functions, or
- A congenital anomaly/birth defect.

Important medical events that may not result in death, be life-threatening, or require hospitalization may be considered serious when, based upon appropriate medical judgment, they may jeopardize the patient or subject and may require medical or surgical intervention to prevent one of the outcomes listed in this definition. Examples of such medical events include allergic bronchospasm requiring intensive treatment in an emergency room or at home, blood dyscrasias or convulsions that do not result in inpatient hospitalization, or the development of drug dependency or drug abuse.

This definition of an SAE permits either the sponsor or the investigator to decide if an event is serious. Because SAEs are critically important for the identification of significant safety problems, FDA believes taking into account both the investigator's and the sponsor's assessment is important. For example, the investigator's perspective may be informed by having actually observed the event, and the sponsor is likely to have broader knowledge of the drug and its effects to inform its evaluation of the significance of the event. If either the sponsor or investigator believes that the event is serious, the event must be considered serious and evaluated by the sponsor for possible expedited reporting.

8.3.2.1.3. Time Period and Frequency for Collecting Adverse Event and Serious Adverse Event Information

Collection of AEs and SAEs will begin at the time a subject signs informed consent and continues until the follow-up contact. SAEs that are spontaneously reported by the subject or subject representative or discovered by the investigator or designee after the follow-up visit and up to 30 days after the last dose of investigational product must be collected and reported.

All SAEs will be recorded and reported to Worldwide Clinical Trials or Axovant Sciences within 24 hours of the investigator becoming aware of the SAE.

Investigators are not obligated to actively seek AEs or SAEs in former study subjects. However, if the investigator learns of any SAE, including a death, at any time after a subject has been discharged from the study, and he/she considers the event reasonably related to the investigational product or study participation, the investigator must promptly notify the sponsor or sponsor representative.

8.3.2.1.4. Assessment of Adverse Events

The severity of each AE will be assessed by the investigator, or designee approved and documented for this study, as mild, moderate, or severe based on the below definitions:

- Mild: Event that is usually transient and may require only minimal treatment or therapeutic intervention. The event does not generally interfere with usual activities of daily living
- Moderate: Event that is usually alleviated with additional specific therapeutic intervention. The event interferes with usual activities of daily living, causing discomfort, but poses no significant or permanent risk of harm to the subject.
- Severe: Event that interrupts usual activities of daily living or significantly affects clinical status, or may require intensive therapeutic intervention.

Note that severity is not the same as “seriousness,” which is defined in Section [8.3.2.1.2](#).

Outcome will be assessed using the following categories: recovered/resolved, not recovered/not resolved, recovered/resolved with sequelae, fatal, or unknown.

Instructions for assessing causality are provided in the Study Reference Manual.

8.3.2.1.5. Method of Detecting Adverse Events and Serious Adverse Events

Care will be taken not to introduce bias when detecting AEs and/or SAEs. Open-ended and non-leading verbal questioning is the preferred method to inquire about AE occurrence. Appropriate questions include:

- “How are you feeling?”
- “Have you had any (other) medical problems since your last visit/contact?”
- “Have you taken any new medicines, other than those provided in this study, since your last visit/contact?”

8.3.2.1.6. Follow-up of Adverse Events and Serious Adverse Events

After the initial AE/SAE report, the investigator is required to proactively follow each subject at subsequent visits/contacts. All AEs and SAEs will be followed until resolution, until the condition stabilizes, until the event is otherwise explained, or until the subject is lost to follow-up.

8.3.2.1.7. Reporting of Serious Adverse Events

All new SAEs must be reported in English to the study sponsor or sponsor’s representatives within 24 hours of the investigators first knowledge of the event using the sponsor-supplied Serious Adverse Event Form regardless of relationship to the study procedures or investigational product. All deaths must be reported within 24 hours of the investigator’s first knowledge of the

event. It is recognized that complete information may not be available at the time of the initial SAE report. Additional information should be supplied on subsequent Serious Adverse Event Forms as it becomes available.

For the initial SAE notification report, the investigator must provide, at minimum, basic information such as the protocol number, subject's date of birth, subject identification number, period of investigational product intake, event term, nature of the event, the seriousness criteria, and the investigator's attribution regarding relatedness to investigational product. In addition, the initial SAE report should include all pertinent known information about the SAE and the affected subject. In addition, the investigator should provide a narrative to describe the course of events including any treatments or relevant procedures. Follow-up information, which may include copies of relevant subject records and other documents not available at the initial SAE report must be sent to Worldwide Clinical Trials as soon as available. Follow-up SAE reports may describe the evolution of the reported event and any new assessment of outcome and/or relationship to investigational product. Full supporting documentation should be solicited by the investigative site even if the SAE occurred at another institution. Such documentation may include copies of relevant medical/hospital records, pathology, or autopsy reports.

Additional instructions regarding SAE reporting are provided in the Study Reference Manual.

8.3.2.1.8. Regulatory Reporting Requirements for Serious Adverse Events

Prompt notification by the investigator to the sponsor or sponsor representative of all SAEs and non-serious AEs occurring during a clinical trial is essential so that legal obligations and ethical responsibilities towards the safety of subjects and the safety of a product under clinical investigation are met.

Axovant Sciences has a legal responsibility to notify both the local regulatory authority and other regulatory agencies about the safety of a product under clinical investigation. Axovant Sciences will comply with country-specific regulatory requirements relating to safety reporting to the regulatory authority, Institutional Review Board (IRB)/Independent Ethics Committee (IEC) and investigators.

Investigator safety reports are prepared for suspected unexpected serious adverse reactions (those not listed in the Investigator Brochure) according to local regulatory requirements and Axovant Sciences policy and are forwarded to investigators as necessary.

An investigator who receives an investigator safety report describing an SAE(s) or other specific safety information (e.g., summary or listing of SAEs) from Axovant Sciences will file it with the Investigator Brochure and will notify the IRB/IEC, if appropriate according to local requirements.

8.3.2.2. Safety Monitoring Committee

An independent Safety Monitoring Committee (SMC) will be established by the sponsor to review accumulating study data to monitor the safety of all subjects enrolled in RVT-101-3001

on an ongoing basis. Members of the committee will include clinicians and a biostatistician who are experienced in the conduct and monitoring of clinical studies. No Axovant Sciences employee or investigator involved in the RVT-101-3001 study will be a member of the SMC or participate in closed SMC sessions. However, representatives from Axovant Sciences may attend open meeting sessions and will be available to provide additional information to the SMC as requested.

The SMC will evaluate potential safety and tolerability issues during periodic scheduled reviews of the safety data accrued during the conduct of the study. The content and format of the safety data provided will be in agreement with requests by the SMC members and will contain blinded interim safety data. However, the SMC will be provided unblinded treatment codes for these studies if a significant safety concern is identified. Ad hoc SMC meetings may be held as necessary.

After reviewing the interim safety data from RVT-101-3001, the SMC may make a recommendation to Axovant Sciences to continue the study with or without modification or to terminate the study. All SMC meetings will be properly documented in a SMC report to the sponsor.

SMC membership and responsibilities will be further outlined in the SMC Charter, which will be maintained separately from the protocol.

8.3.2.3. Physical Examinations

Physical examinations will be performed as indicated in Table 2. A complete physical examination will include, at a minimum, assessment of the cardiovascular, respiratory, gastrointestinal, and neurological systems. Neurological examinations will include assessment of gait, balance, coordination, cranial nerves and motor and sensory systems. A brief, symptoms-directed physical examination will include, at a minimum, assessments of the lungs, cardiovascular system, and abdomen (liver and spleen). Physical examinations at Screening and Visit 8 will be full examinations; at all other study visits, an abbreviated physical examination is required.

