Assess investigational product and study-supplied donepezil compliance			X	X	X	X	X	X	X	X	
Physical exam/ current medical conditions ⁴	X	X	X	X	X	X	X	X	X	X	
Complete neurological exam	X		X								
MRI or CT ⁵	X										
12-lead ECG	X	X	X	X	X	X	X	X	X	X	
Vital signs ⁶	X	X	X	X	X	X	X	X	X	X	
Review adverse events		X	X	X	X	X	X	X	X	X	
Serum OR urine pregnancy test ⁷	X										
Hep B, and Hep C screen ⁸	X										
TSH, vitamin B ₁₂ , syphilis serology ⁹	X										
Serum chemistry	X	X	X	X	X	X	X	X	X	X	
Hematology	X	X	X	X	X	X	X	X	X	X	
Urinalysis	X	X	X	X	X	X	X	X	X	X	
Blood alcohol content	X	X	X	X	X	X	X	X	X	X	
RVT-101 level ¹⁰					X	X	X	X	X	X	
Donepezil level ¹⁰			X			X		X			

Study Period: Study Visit Number: Study Week:	Screening V1 W(-7)	Run-in V2 W(-3)	Baseline V3 ¹ W0	Treatment						Follow-up ¹¹ V9 W26	ET ET
				V4 W3	V5 W6	V6 W12	V7 W18	V8 W24	V9 W26		
Study Day: relative to Baseline unless specified	Up to 28 days before V2	21 + 5 days ^{1,2} before V3	0	21 ± 3	42 ± 3	84 ± 5	126 ± 5	168 ± 5	14 to 19 days after last dose of IP		
Hachinski Ischaemia Scale	X										
ADAS-Cog		X	X	X	X	X	X	X			
MMSE	X		X								
ADCS-ADL		X	X	X	X	X	X	X			
CIBIS			X								
CIBIC+						X	X	X			
NPI			X			X	X	X			
DS			X					X			
RUD Lite			X					X			
EQ-5D			X					X			

Abbreviations: ADAS-Cog = Alzheimer's Disease Assessment Scale – cognitive subscale; ADCS-ADL = Alzheimer's Disease Cooperative Study Group – Activities of Daily Living Inventory; CIBIC+ = Clinician's Interview-Based Impression of Change Plus caregiver Interview; CIBIS = Clinician's Interview-Based Impression of Severity; C-SSRS = Columbia Suicide Severity Rating Scale; CT = computed tomography; DS = Dependence Scale; ECG = electrocardiogram; ET = early termination; EQ-5D = EuroQOL 5 dimensions questionnaire; Hep = hepatitis; MMSE = mini-mental state examination; MRI = magnetic resonance imaging; NPI = Neuropsychiatric Inventory; RUD Lite = Resource Utilization in Dementia Lite; TSH = thyroid stimulating hormone; V = visit; W = week.

Notes:

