1. The Single-Blind Run-In Period may be extended for 3 weeks after discussion with the Medical Monitor for subjects who do not meet MMSE stability criterion for randomization in the event that the change in MMSE is seen in the setting of recent change in AD therapy. Subjects requiring this run-in extension period will have a new baseline visit window of no more than 21 to 24 days after the originally intended baseline. This subsequent visit will then serve as the subject's baseline if randomization criteria are met. No new study drug or study-supply donepezil will be dispensed for the additional run-in period; subjects should be instructed to continue taking blinded investigational product and study supply donepezil dispensed at Visit 2.
2. The ADAS-Cog assessment will be the first assessment performed, followed by the MMSE. If the MMSE score does not meet the stability criterion for randomization, no other assessments should be performed. If after discussion with the Medical Monitor it is determined that the Single-Blind Run-In Period may be extended by 3 weeks per the criterion above, the subject should be scheduled to return to the clinic in 3 weeks' time, and all baseline assessments should be performed at this repeat visit (refer to footnote 1).
3. No new drug will be dispensed at V4. The bottles and pill count should be checked for compliance at V4, but no new medication will be dispensed at that visit.
4. Physical examinations at Screening and V8 will be full examinations; at all other study visits, an abbreviated physical examination is required.
5. MRI or CT scan will be performed between V1 and V2 if no scan has been performed within the previous 12 months. These scan findings must be consistent with the diagnosis of dementia due to AD without any other clinically significant pathologies.
6. Vital signs will include systolic blood pressure, diastolic blood pressure, heart rate, respiratory rate, temperature, and body weight at each visit and height at screening. Postural changes in blood pressure will be assessed at screening.
7. Required only for women of child bearing potential.
8. If these tests were performed within 3 months prior to the planned first dose of investigational product, testing is not required. Records must be present in the subject's source documents.

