10.4.7.3. Vital Signs, Electrocardiograms, Physical Findings, and Other Safety Evaluations

Descriptive summaries of medical history, vital signs, weight, and ECG parameters will be presented separately for each study visit and treatment group. Clinically significant abnormal morphological ECG findings will be summarized by study visit.

Abnormal physical examination findings will be summarized to include the number and percentage of subjects experiencing each treatment-emergent abnormal physical finding.

Concomitant medications will be coded using the WHO ATC classification (http://www.whocc.no/filearchive/publications/1_2013guidelines.pdf).

These data will be summarized by treatment group.

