**Table 1: Examples of Patterns of Missingness (Study RVT-101-3001)**

Pattern	Treatment Group	Number (%) of Patients	Baseline	Week 3	Week 6	Week 12	Week 18	Week 24
1	Intepirdine	xx (xx.x%)	X	X	X	X	X	.
	Placebo	xx (xx.x%)	X	X	X	X	X	.

Pattern	Treatment Group	Number (%) of Patients	Baseline	Week 3	Week 6	Week 12	Week 18	Week 24
2	Intepirdine	xx (xx.x%)	X	X	X	X	.	.
	Placebo	xx (xx.x%)	X	X	X	X	.	.
Etc.								

In addition, a comparison of dropout due to AE will be performed between the treatment groups, along with a graphical display of the time to discontinuation due to AE by treatment group.

A concern indicated by CHMP was relating to considerable dropout. However, the actual dropout in this study is estimated to be no higher than 11%. An examination of the patterns of missing data for the co-primary endpoints demonstrates that missing data are rare, and that collection of the endpoints was, in general, thorough, and that over 87% of patients had at least one of their Week 24 co-primary efficacy endpoints collected. Further, dropout (discontinuation) due to adverse event is estimated to be less than 4%, and dropout due to lack of efficacy less than 1%. Therefore, the overwhelming majority (~95%) of Week 24 values will either be collected or will be attributed to MAR. These outcomes reflect a high level of study oversight and management of patient visits as well as patient retention to minimize the effects of missing values on the primary targets of estimation. Further, the methods proposed for the primary analysis (MMRM) are recognized as robust under these assumptions.

Data collection beyond premature (early) discontinuation was not performed in this study, while the number of patients with missing values at Week 24 is low, patients discontinuing early did not have their later efficacy data collected. Relating to this, CHMP indicated:

- “A more appropriate primary target of estimation could make use of information observed after a patient withdrew from randomized treatment. Patients starting a new medication or have their background medication changed after withdrawal should also be followed and included in the analysis, as a comparison of treatment policies would also be of interest.”

As collection of post-drop data was not performed, the alternative option to address these missing values will be pursued. To address this situation, CHMP suggested:

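### Subjects who stop early are not routinely examined for new neurological signs, because the Early Termination Visit carries only the abbreviated physical examination

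*Protocol*

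**What the plan says.** Protocol Section 8.3.2.3 sets the timing: "Physical examinations at Screening and Visit 8 will be full examinations; at all other study visits, an abbreviated physical examination is required". Note 4 to Table 2 (Section 8.1) gives the same rule: "Physical examinations at Screening and V8 will be full examinations; at all other study visits, an abbreviated physical examination is required". Table 2 marks a physical examination in every visit column, including Early Termination.

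Section 8.3.2.3 also sets the content. For the full examination: "A complete physical examination will include, at a minimum, assessment of the cardiovascular, respiratory, gastrointestinal, and neurological systems". For the shorter one: "A brief, symptoms-directed physical examination will include, at a minimum, assessments of the lungs, cardiovascular system, and abdomen (liver and spleen"). The section schedules *full* and *abbreviated* examinations but describes *complete* and *brief* ones. I read these as the same two types.

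For reporting, Section 10.4.7.3 plans a summary of "the number and percentage of subjects experiencing each treatment-emergent abnormal physical finding". Section 10.4.7 bases safety analyses on the Safety Population, which Section 10.3.1 defines as everyone randomized who took at least one dose. Early stoppers are therefore included. Section 10.4.7.3 itself names no denominator.

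**The concern.** A completer has one examination on treatment that must include the neurological system. An early stopper has none. The two groups are then tabulated together, so the chance that a new sign is found depends on whether the subject reached Week 24.

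This matters more than usual for two reasons. RVT-101 acts in the central nervous system (Section 3.1.2), so gait, balance, coordination and motor signs are of direct interest. And adverse events are among the listed reasons for withdrawal (Section 6.6.1), so stopping may be related to the findings being looked for. At stake is the completeness of one descriptive safety table.

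**Working it through.** **Which visits carry which examination**

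| Visit | Physical examination | Neurological system required? |
|---|---|---|
| Screening | full | yes |
| Visits 4 to 7 | abbreviated | no, unless symptoms direct it |
| Visit 8 (Week 24) | full | yes |
| Early Termination | abbreviated | no, unless symptoms direct it |
| Visit 9 | abbreviated | no, unless symptoms direct it |

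Of the five scheduled on-treatment visits (4 to 8), one requires the neurological part. Visit 9 does not close the gap: Section 8.1 requires it of subjects who complete double-blind treatment and do not enter the extension. Further safety follow-up after stopping depends on the subject's agreement (Section 6.6.1).

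Table 2 also has a separate row, "Complete neurological exam". In the text available to me its marks fall at Screening and Baseline only, but the table is visibly damaged: the dispensing rows show only Visits 2 and 3, while Sections 7.1 and 8.1 also name Visits 5, 6 and 7. I place no weight on that row. Section 8.3.2.3 and note 4 are enough.

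**How many subjects**

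The plan gives no figure for examination findings. The one linked figure is the total randomized (Section 10.2), which reproduces: 435 / (1 − 0.25) = 580 per arm, or 1160 in total, against approximately 1150 stated (0.9% apart).

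- At the dropout in SAP addendum Section 3.2.3.1, where "the actual dropout in this study is estimated to be no higher than 11" per cent: 1150 × 0.11 = 126.5, so at most about 127 (about 63 per arm).
- At the planning figure in Section 10.2: 1150 × 0.25 = 287.5, so about 288 (about 144 per arm). That 25% also allows for missing data, so it overstates early stopping.

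**What this could do to the percentage**

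Let *d* be the proportion stopping early, *q* the true rate of a given sign in stoppers, and *s* the chance that a sign in a stopper is still found, taking detection in completers as 1. Then

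shortfall in percentage points = (1 − *s*) × *d* × *q*

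Only *d* comes from the documents. The values of *q* and *s* below are assumptions that show the range.

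| *d* | *q* | *s* = 0 | *s* = 0.5 | *s* = 1 |
|---|---|---|---|---|
| 11% | 5% | 0.55 | 0.275 | 0 |
| 11% | 15% | 1.65 | 0.825 | 0 |
| 25% | 5% | 1.25 | 0.625 | 0 |
| 25% | 15% | 3.75 | 1.875 | 0 |

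The column *s* = 0 is a bound, not a forecast, because the abbreviated examination follows symptoms. Applying 15% to all stoppers is also harsh: the addendum puts discontinuation for adverse events below 4% and for lack of efficacy below 1%.

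**The case against.** A reader might infer that an early stopper can never show a treatment-emergent neurological finding. The documents do not support that. The shorter examination is directed by symptoms, and its list of systems is a minimum. A subject who reports unsteadiness can be examined for it at Early Termination, and the finding recorded.

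There is also a second route. Section 8.3.2.1.1 has clinically significant examination findings recorded as adverse events. Table 2 schedules adverse-event review throughout treatment and at Early Termination. Section 10.4.7.1 summarizes events leading to discontinuation separately. A subject who stops because of a neurological event therefore appears in the main safety tables.

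Nor is the denominator settled. The Safety Population is implied by Section 10.4.7 but not stated for this table. The main SAP of August 9, 2017 is not among the documents, only its addendum, and the main SAP may say more.

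All of this stands, and it narrows the point to signs that nobody complains of or that are not judged clinically significant. It does not remove it. With baseline MMSE scores of 10 to 26, detection that waits for a complaint relies heavily on the subject and caregiver noticing. The adverse-event definition also leaves out expected progression of existing disease. A sign that would be looked for at Visit 8 can pass unseen at Early Termination.

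**Conclusion.** The point holds in a narrow form. Early stoppers, at most about 127 of 1150 at 11% or about 288 at 25%, have no mandatory neurological examination after dosing, and completers have one. The table in Section 10.4.7.3 may therefore under-count asymptomatic signs in early stoppers. The documents give neither the rate of such signs nor the chance of finding them at an abbreviated examination, so the size cannot be estimated. The table under the working shows only how it scales.

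A reader might go further and infer that the arm comparison could change direction. That would need dropout differing between arms, a raised rate of signs in stoppers and little or no detection at Early Termination. The documents supply none of these figures, and symptom-directed examination argues against the last. If dropout, detection and the relative rate in stoppers are the same in both arms, the risk ratio is unchanged and only the percentages and their difference shrink.

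The protocol does not contradict itself here: the text and the table note agree. No efficacy result, sample size or main adverse-event table is affected. This is a cheap improvement, not a flaw in the trial's conclusions.

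**What to change.** 1. Change Section 8.3.2.3 and note 4 to Table 2 so that the full physical examination is required at Screening, Visit 8 and Early Termination. Early Termination already includes a physical examination, so the cost is a few more minutes in the subjects who attend it. It cannot help with subjects who are lost before that visit.
2. In Section 10.4.7.3, or the SAP safety section, keep the Safety Population percentages and report beside them, per arm, the number of subjects examined after baseline for each body system. This costs one sentence and one extra row per system.
3. Do not restrict the denominator to subjects with a full post-baseline examination. Under the present schedule that means subjects who reached Visit 8. It would condition on completion, an outcome after randomization, and would discard real findings made at a symptom-directed Early Termination examination.

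On timing, the addendum (Section 1) places the end of the trial in late September 2017. By then the visit change could reach few or no subjects, but the reporting change could still be specified before unblinding.
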